11.2.7. Reporting of Serious Adverse Event(s) to Sponsor

All AEs must be assessed by the Investigator to determine if they meet criteria for an SAE. All SAEs must be reported to the Sponsor or its representative immediately or within 24 hours of the Investigator or their staff becoming aware of the event regardless of the presumed relationship to the study drug.

The Investigator must verify the accuracy of the information recorded on the SAE pages of the SAE report with the corresponding source documents, and submit the SAE report electronically via the Rave Safety Gateway as applicable. If the eCRF is not available, the Investigator must complete the Contingency SAE paper report, sign and date SAE pages and send a copy via email or fax to the contact information provided below:

When further information becomes available, the SAE report should be updated with the new information and reported immediately via the same method as the initial report. Additional follow-up information, if required or available, should be entered into the eCRF and sent to the Sponsor or designee within 24 hours of the Investigator or study site staff becoming aware of this additional information. These reporting timelines should be followed for all initial and follow-up SAEs.

For all SAEs the Investigator must provide the following:

- Appropriate and requested follow-up information in the time frame detailed above
- Causality of the serious event(s)
- Outcome of the serious event(s)
- Medical records and laboratory/diagnostic information

11.2.8. Exposure During Pregnancy and Lactation

Pregnancy data will be collected during this trial for all subjects.

For all Alexion products, both in development or post approval, exposure during pregnancy must be recorded and followed. Exposure during pregnancy, also called exposure *in utero* (EIU), can be the result of either maternal exposure or transmission of drug product via semen following paternal exposure.

If a subject within this trial or a subject's partner becomes or is found pregnant while treated or exposed to study drug, the Investigator must submit the "Pregnancy Reporting and Outcome/ Breast Feeding Form" to the Sponsor or its delegate via the same method as SAE reporting.

The subject should be followed until the outcome of the pregnancy is known (spontaneous miscarriage, elective termination, normal birth or congenital abnormality), even if the subject discontinued study drug or discontinued from the trial. When the outcome of the pregnancy becomes known, the form should be updated and returned to the Sponsor or its delegate. If additional follow-up is required, the Investigator will be requested to provide the information.

Pregnancy in itself is not regarded as an AE unless there is a suspicion that the Investigational Product may have interfered with the effectiveness of a contraceptive medication. However, complications of pregnancy and abnormal outcomes of pregnancy are AEs and many may meet criteria for an SAE. Complications of pregnancy and abnormal outcomes of pregnancy such as ectopic pregnancy, spontaneous abortion, intrauterine fetal demise, neonatal death or congenital anomaly would meet criteria of an SAE and thus, should be reported as an SAE. Elective abortions without complications should not be handled as AEs.

Exposure of an infant to an Alexion product during breast feeding should also be reported on the "Pregnancy Reporting and Outcome / Breast Feeding Form", and any AEs an infant may experience following breast feeding must be reported to the Sponsor or its delegate.

11.2.9. Reporting Requirements

This protocol will use the current Investigators Brochure as the Reference Safety Document. The expectedness and reporting criteria of an SAE will be determined by the Sponsor from the Reference Safety Document.

11.2.9.1. Sponsor

The Sponsor or its legal representative is responsible for notifying the relevant regulatory authorities of SAEs meeting the reporting criteria as per regional and local regulations.

11.2.9.2. Investigator

Investigator must fulfill all local regulatory obligations required for study investigators. It is the PI's responsibility to notify the Institutional Review Board (IRB) or Independent Ethics Committee (IEC) of all SAEs that occur at his or her site. Investigators will also be notified of all unexpected, serious, drug-related events (7/15 Day Safety Reports) that occur during the clinical trial. Each site is responsible for notifying its IRB or IEC (if local) of these additional SAEs according to local regulations.

12. PHARMACOKINETIC AND PHARMACODYNAMIC ASSESSMENTS

12.1. Blood Sample Collection

Table 5 summarizes blood sample collection time points for PK and PD assessments for the study based on frequency of ALXN1007 dosing (ie, weekly or twice weekly). At the time of sample collection, actual blood sampling dates and times must be recorded.

The central laboratory will supply established or generally acknowledged methods and shipping instructions.

12.2. Pharmacokinetic and Pharmacodynamic Sample Analysis

Blood samples will be collected and plasma assayed for ALXN1007 concentration. The actual blood sampling times will be used in calculations for PK parameter estimation.

For those patients entering this study less than 4 weeks after receiving another investigational drug, baseline plasma concentrations of the other investigational drug may be assayed. No additional samples will be collected; aliquots from the baseline ALXN1007 PK samples will be used for this assessment if performed.

The PD effects of ALXN1007 will be determined by assessing plasma concentrations of biomarkers, which may include C3, C4, C5a, C5 and sC5b-9. Serum terminal complement activity may be measured by the cRBC hemolysis and WieslabTM CCP assays.

12.3. Exploratory Biomarker Assessments

Biopsy specimens may be evaluated for complement deposition or for immune cell characterization by immunohistochemistry (IHC).

Blood samples will be collected prior to dosing at Baseline, Days 7, 28 and 49; and at Day 86 and Day 180 (or at the ET visit, if a subject prematurely discontinues or is withdrawn from the study). These samples may be used to characterize changes from Baseline in the levels of biomarkers associated with alternative complement pathways activation or of mechanistic biomarkers thought to be associated with the development of GI GVHD. Pharmacodynamic effects on complement may include, but are not limited to, assessments of plasma Ba and Bb. Additional biomarkers associated with GVHD and downstream effects of complement activation may include, but are not limited to, TNFR1, ST2 and REG3a. Additional exploratory analyses, including anti-factor H antibody titer, may be performed.

Detailed instructions for sample collection, preparation and handling will be supplied in a Laboratory Manual.

12.4. Optional Pharmacogenetic Assessment

For subjects who sign an additional optional consent, a blood sample will be drawn at Baseline for pharmacogenetic (PGx) research to better characterize genetic variability that may affect efficacy or safety endpoints, or the GI GVHD disease process, such as mutations in genes that

regulate the complement pathway. These samples may be used for future exploratory bioanalytical or PGx tests to better understand potential complement-associated genetic mutations as well as the pathogenesis, course, and outcome of GI GVHD.

If permitted, according to local regulations, blood may be used for additional GI GVHD or complement associated genetic analysis from subjects who have consented to this optional component of the clinical study. Refusal to participate will not result in ineligibility for the main part of the clinical study. Blood or DNA samples may be used for analysis of candidate genes believed to be associated with GI GVHD or complement pathways in order to develop improved diagnostic or therapeutic methods. Blood or DNA samples may also be stored for future testing of additional genes that, at a later date, are discovered or found to be associated with GI GVHD, complement signaling pathways, or with the PK or PD of ALXN1007. Additional genotyping will only be performed if it is believed or hypothesized by the Sponsor that such genetic analysis might help clarify issues with the clinical data. No other genetic analysis will be performed and the stored samples will not be used for any other purpose.

Additional information regarding the stored samples is outlined in Section 17.2.

The IRB/IEC and, where required, the applicable regulatory agency, must approve the PGx assessments before these can be conducted at the study site. The approval(s) must be in writing and clearly specify approval of the PGx assessments. In some cases, approval of the PGx assessments can occur after approval is obtained for the rest of the study. If so, then the written approval will clearly indicate that approval of the PGx assessments is being deferred and the study, except for PGx assessments, can be initiated. When the optional PGx assessments are not approved, this will be clearly indicated in the approval for the clinical study.

13. STATISTICS

This section provides a summary of the statistical analyses that will be completed for this study. Additional details for the statistical analyses will be described in detail in the SAP.

13.1. General Considerations

All data collected during the study will be presented in summary tables, figures and/or by-subject data listings. Continuous variables will be summarized using mean, standard deviation (SD), median, minimum and maximum. Categorical variables will be summarized using percentages and frequency distributions. Graphical displays will be presented as appropriate.

A stopping rule for excess mortality at Day 56 will be applied after every 6 subjects are accrued. The stopping guidelines for excess mortality will be applied as described in Section 6.5.4.

A brief interim safety report summarizing AEs and SAEs will be generated when the first six subjects have completed the day 86 visit. Additionally, an informal interim analysis will occur after all subjects have completed Day 56, which is the end of the treatment period. This interim analysis will summarize the primary endpoint and other efficacy endpoints with the exception of overall survival and non-relapse mortality. In terms of safety, all treatment emergent adverse events (TEAEs), infections, neutropenia and infusion reactions will be summarized. The interim analyses will also summarize PK and PD results. Additional informal interim analyses may be conducted based on regulatory requests and/or Sponsor discretion. A final analysis will be conducted at study completion.

Efficacy and safety analyses will be performed using SAS for Windows, Version 9.2 or higher (SAS Institute Inc., Cary, NC, USA).

No formal hypothesis testing will be performed. Efficacy data will be analyzed using descriptive statistics. All analysis tabulations will be presented by dose across the full range of doses actually examined in the study.

13.2. Determination of Sample Size

Up to 36 subjects confirmed by biopsy to have acute GI GVHD will be enrolled in this study. This sample size is felt to be sufficient for assessment of safety, tolerability, PK/PD, and efficacy of ALXN1007 at doses ranging from 10 mg/kg per week up to 40 mg/kg per week in patients with acute GI GVHD.

13.3. Analysis Population

Safety analyses will be performed on the Safety Set and on the modified Safety Set, as specified in the SAP. The Safety Set is defined as all subjects who receive at least 1 dose of ALXN1007. The modified Safety Set is defined as all subjects who receive at least 1 dose of ALXN1007 and for whom GI GVHD is confirmed through biopsy. PK and PD analyses will be performed on all subjects who receive at least 1 dose of ALXN1007 and who have evaluable PK and PD data.

Efficacy analyses will be performed on the modified Full Analysis Set (mFAS) as well as on a Per Protocol (PP) set. The mFAS will include all subjects who receive at least 1 dose of

ALXN1007 and for whom GI GVHD is confirmed through biopsy. The PP set is a subset of the mFAS and will include all subjects who have no major protocol deviation(s) that might potentially affect efficacy. The PP set will be fully described in the SAP, and subjects identified prior to database lock.

13.4. Demographics and Baseline Characteristics

All demographic, baseline characteristics and medical history data will be summarized using the following sets: mFAS, PP and Safety Populations. For categorical variables, frequencies and percentages will be presented. Continuous variables will be summarized using descriptive statistics (mean, median, SD, and minimum and maximum).

13.5. Subject Disposition and Treatment Compliance

The number of subjects screened, treated and included in the safety and efficacy analysis sets will be tabulated by counts and percentage of subjects. Reasons for any subject withdrawals will be provided.

Treatment compliance with ALXN1007 will be presented for all subjects.

13.6. Prior and Concomitant Medications and Therapies and Hematopoietic Cell Transplantation Information

Prior and concomitant medications and therapies will be summarized using the Safety Set and the modified Safety Set. Prior medications are defined as medications taken prior to the first dose of ALXN1007. Concomitant medications are defined as medications taken after the first dose of ALXN1007.

Doses of methylprednisolone will be converted to prednisone equivalents by multiplying the methylprednisolone dose by 1.25. Prednisone doses for each subject will be converted to mg/kg. The cumulative and average corticosteroid doses will be calculated through Days 28, 56, 86 and 180.

Medications will be coded using the World Health Organization Drug Dictionary (WHODrug). Medication summaries will be presented by WHODrug Anatomical Therapeutic Chemical (ATC) and by WHODrug generic name.

All HCT information collected, including the conditioning regimen received in preparation for HCT and post-transplant GVHD prophylaxis regimen, will also be summarized and listings provided.

13.7. Efficacy Analyses

Efficacy will be performed on the mFAS and the PP sets, as described in the SAP.

13.7.1. Overall Acute GVHD Response Rate

The proportion of subjects with overall response will be summarized by visit and 95% CIs will be calculated. Subjects who discontinue from the study early will be imputed as having no response.

13.7.2. Acute GI GVHD Response Criteria

Acute GI GVHD response criteria will be based on the proportion of subjects with CR, PR, MR, NR and Progression and will be summarized by visit along with 95% CIs.

Subjects who discontinue from the study early will be imputed as having no response.

13.7.3. Acute GVHD Response Criteria (All Organs)

Response for all organs involved with acute GVHD will be based on the proportion of subjects with CR, PR, MR, NR and Progression and will be summarized at Days 14, 28 and 56. The proportion of subjects with VGPR will be summarized at Days 14, 28 and 56, and 95% CIs will be calculated.

Subjects who discontinue from the study early will be imputed as having no response.

13.7.4. Treatment Failures

The proportion of subjects who meet the treatment failure criteria will be summarized at Days 14, 28 and 56 along with 95% CIs. Subjects who discontinue from the study early will be considered treatment failures.

13.7.5. Overall Survival

Overall survival will be summarized using date of first study treatment with ALXN1007 up to Days 180 and 360 via the use of the Kaplan-Meier method, and 95% CIs will be calculated.

Subjects who are still alive as of the last known follow-up will be right censored as of the date of last subject contact.

13.7.6. Acute GVHD Flares

Cumulative incidence of acute GVHD flares using date of first study treatment with ALXN1007 (Baseline) through Day 86 will be estimated using competing risk survival analysis methods to account for death as a competing risk. Point estimates and 95% CIs will be provided. Subjects who do not experience acute GVHD flares will be right censored as of the date of last subject contact.

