^{*} Screening period for the study will be initiated after informed consent form signing (ie, subject enrollment). Acute GI GVHD staging at the time of diagnosis (that can be made up to 7 days prior to the first ALXN1007 dose) will be captured and used for comparison to post-Baseline GVHD staging to assess treatment response.

^{**} With approval of Amendment 6, Cohort 2 (20 mg/kg QW for 8 weeks) will be added to the study. An additional cohort (Cohort 3, 20 mg/kg twice weekly for 8 weeks), is planned after DMC review of safety and tolerability data at Day 28 on the first 3 patients in Cohort 2. At the discretion of the Sponsor, and in consultation with the DMC, other dosing cohorts (not to exceed a total dose of 40 mg/kg per week for 8 weeks) may also be explored based on cumulating safety and tolerability data as well as any PK/PD data that may be available.

^{***} Follow-up period for the study consists of study visits at Weeks 12 (Day 86) and 26 (Day 180), with telephone contact at Week 52 (Day 360) for survival status only.

Table 3: Schedule of Events for Subjects on a Once Weekly ALXN1007 Dosing Schedule

Procedures and Evaluations	Screening	Treatment (± 2 days)										Follow-up (± 15 days, except for ET)			
Weeks		0	1	2	3	4	5	6	7	8	12	26		52	
Days	-3 to -1	Baseline	7	14	21	28	35	42	49	56	86	180	ET	360	
Informed Consent	X														
Eligibility - Inclusion/Exclusion Criteria	X	X^1													
Medical History, Demographics	X														
ALXN1007 Administration ²		X	X	X	X	X	X	X	X						
Acute GVHD Staging ³	X	X	X	X	X	X	X	X	X	X	X	X	X		
Antibiotic Prophylaxis Against Meningococcal Infection ⁴	X	X	X	X	X	X	X	X	X	X	X ⁴		X ⁴		
Physical Exam ⁵	X					X				X		X	X		
ECG		X^6				X^6				X		X	X		
Vital Signs ⁷	X	X	X	X	X	X	X	X	X	X	X	X	X		
Weight	X	X	X	X	X	X	X	X	X	X	X	X	X		
Stool Clostridium difficile Testing (Local lab)	X														
CSA, Tacrolimus, and/or Sirolimus Levels (if needed) ⁸		X	X		X		Х		X				X		
CMV-PCR		X	X	X	X	X	X	X	X	X			X		
Routine Laboratory Test ⁹	X	X	X	X	X	X	X	X	X	X	X	X	X		
Creatinine Clearance (local lab)	X														
ANC (local lab)	X														
Endoscopy of Upper and/or Lower GI Tract / Biopsy ¹	X														
CPK, Thyroid Function Tests (Central lab)		X	X			X				X	X	X	X		

Table 3: Schedule of Events (Continued)

Procedures and Evaluations	Screening		Treatment (± 2 days)							Follow-up (± 15 days, except for ET)				
Days	-3 to -1	to -1 Baseline 7 14 21 28 35 42 49 56	56	86	180	ET	360							

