6.1.6. Missing Visits

Subjects who are unable to complete a scheduled visit must be contacted by the site study staff to determine the reason. For subjects who miss a dose, the Investigator is responsible for discussing the status and future treatment of these subjects with the Alexion Medical Monitor. Every effort must be made to undertake the protocol-specified evaluations through Day 180.

Follow-up due diligence and documentation are discussed in Section 7.3.2.

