7.3.2. Handling of Withdrawals and Discontinuation from Study Treatment

The following procedures will be followed when a subject withdraws or is withdrawn from study participation:

- If the subject withdraws consent prior to the Day 180 visit, the ET visit should be performed for safety at the time of consent withdrawal (within 5 days), if subject allows.
- Subjects must continue antibiotic prophylaxis active against meningococcal infection for 6 weeks after the last dose of ALXN1007.

• The reason(s) for withdrawal will be recorded in the subject's source documents and the eCRF.

The following procedures will be followed when an investigator discontinues a subject from study treatment:

- In the event of early discontinuation from study treatment, subjects will be requested to return for the remainder of the scheduled study visits through the Day 180 visit.
- In the event that the biopsy results do not confirm GI GVHD, study treatment will be discontinued and an ET visit will be performed 6 weeks (+/- 5 days) after the last dose of ALXN1007 was received.
- If a subject discontinues study treatment due to an AE, the event will be followed until it is resolved or, in the opinion of the PI, the subject is determined to be medically stable. Subjects will be requested to return for the remainder of the scheduled study visits through the Day 180 visit.

For female subjects who become pregnant, please refer to Section 7.3.1.

Subjects who fail to return for final assessments will be contacted by the site study staff members in an attempt to have the subjects comply with the protocol. As it is vital to obtain follow-up data, every effort must be made to undertake protocol-specified follow-up procedures. Follow-up due diligence documentation will consist of 3 phone calls followed by 1 registered letter to the subject's last known address. Refer to the SOM for additional information.

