10.2.4. GVHD Flares

Flares are defined as any progression of acute GVHD through Day 86 after an initial response (ie, earlier CR or PR) that require re-escalation of corticosteroid dosing (ie, administration of ≥2.5 mg/kg/day of prednisone [or methylprednisolone equivalent of 2 mg/kg/day] for at least 2 consecutive days starting on or after Day 5), or initiation of additional topical or systemic therapy for GVHD.

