13.7.7. Discontinuation of Immunosuppressive Medication

Cumulative incidence of discontinuation of all immunosuppression by Days 28, 56, 86 and 180 post-first study treatment with ALXN1007 will be analyzed using similar methods as described above for acute GVHD flares with death as a competing risk.

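### Protocol 13.7.6 censors flare-free subjects at last contact rather than last GVHD staging, so unstaged time before Day 86 can be counted as flare-free and flare incidence can only be understated

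*Protocol*

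**What the plan says.** Flares through Day 86 are one of the other efficacy endpoints (Protocol 5.2.2). Protocol 10.2.4 opens the definition with "Flares are defined as any progression of acute GVHD through Day 86 after an initial response (ie, earlier CR or PR) that require" and then names steroid re-escalation or added topical or systemic therapy. Recognising a flare therefore takes organ staging and a treatment record.

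Protocol 13.7.6 plans a cumulative incidence "using date of first study treatment with ALXN1007 (Baseline) through Day 86 will be estimated using competing risk survival analysis methods", with death as the competing risk, and adds: "Subjects who do not experience acute GVHD flares will be right censored as of the date of last subject contact". Protocol 13.7.5 uses the same censoring date for overall survival. Protocol 13.7.7 analyses discontinuation of immunosuppression with "similar methods as described above for acute GVHD flares with death as a competing risk", and 13.7.8 refers non-relapse mortality to the flare methods too.

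Staging and concomitant medications are scheduled at visits (Tables 3 and 4). Other contacts are not visits:

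- Day 360 (Figure 1 footnote): "with telephone contact at Week 52 (Day 360) for survival status only".
- Missed visits (6.1.6): "Subjects who are unable to complete a scheduled visit must be contacted by the site study staff to determine the reason".
- Failure to return for final assessments (7.3.2): "Follow-up due diligence documentation will consist of 3 phone calls followed by 1 registered letter".

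Two provisions limit the gap. After early discontinuation of treatment, "subjects will be requested to return for the remainder of the scheduled study visits through the Day 180 visit" (7.3.2). A subject who leaves the study before Day 180 has an early termination visit with staging and medications, if possible (6.1.5).

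The SAP keeps the flare definition (5.1.2.5) but states that flares will not be analysed for the abbreviated report. It reduces immunosuppression discontinuation to a listing (5.1.2.6). It gives no flare censoring rule of its own.

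**The concern.** Last contact is the right censoring date for survival, because any contact shows that the subject is alive. It does not show that the subject has had no flare. Neither document equates contact with staging or asks about flares by telephone.

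Take a subject last staged on Day 21 who is alive at the Day 360 call. Under 13.7.6 this subject stays in the risk set, flare-free, through Day 86. Days 21 to 86 were never observed for flares, yet they count as event-free time. Through 13.7.7 the same subject would be carried as still on immunosuppression.

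At stake is a secondary descriptive estimate that errs in the favourable direction.

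**Working it through.** There is no plan figure to reproduce. The documents state no flare rate, no rate of stopping visits and no precision target for this endpoint, so all rates below are assumptions.

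**Direction.** When a subject is censored, the Aalen-Johansen estimator shares that subject's probability mass among those still at risk, some of whom go on to flare. If the subject is held flare-free to Day 86 instead, the mass stays with a non-event. The flare estimate cannot rise. In 5,000 random data sets, moving censoring dates from earlier times to Day 86 never raised it (smallest difference 0.0).

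**Fixed example, N = 18 (the Cohort 1 maximum).** Flares on Days 35, 42, 49, 60 and 70; deaths on Days 20, 40 and 55; three subjects last staged on Day 28 and telephoned after Day 86; seven staged flare-free to Day 86.

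- Last-contact rule: nobody is censored before Day 86, so each flare carries 1/18. Incidence = 5 × 1/18 = 27.8%.
- Last-staging rule: after the Day 20 death, 17/18 of the mass remains. After three are censored on Day 28, 14 subjects share it, each carrying (17/18)/14 = 0.0675. Incidence = 5 × 0.0675 = 33.7%.

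The difference is 5.9 points. The example is unfavourable by design, since all three stop before the first flare.

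**Simulation.** Constant hazards; 20% mortality by Day 86; the stated fraction stops staging at a uniform time between Days 7 and 56, and all of them are reached later; 1,500 replicates. Each cell shows the mean with complete observation → the mean under last-contact censoring, in percent, for N = 18.

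| Assumed flare incidence | 5% stop | 10% stop | 20% stop | 30% stop |
|---|---|---|---|---|
| 20% | 20.0 → 19.4 | 20.0 → 18.7 | 20.1 → 17.8 | 19.7 → 16.4 |
| 30% | 30.2 → 29.4 | 29.9 → 28.1 | 30.0 → 26.6 | 29.7 → 24.8 |
| 40% | 40.1 → 38.9 | 39.5 → 37.4 | 40.0 → 35.7 | 40.0 → 33.5 |

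N = 36 gives nearly the same differences. Over both sizes the understatement is about 0.5-1.2 points at 5% stopping, 1.2-2.1 at 10%, 2.3-4.3 at 20% and 3.3-6.5 at 30%. Censoring at last staging returns the complete-data value to within about 0.1 point, because stopping is unrelated to flare risk in this model.

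**Why the replacement wording matters.** The Day 86 visit has a ±15-day window, Days 71 to 101, and the staging before it is on Day 56. A rule that used the last staging on or before Day 86 would censor a flare-free subject seen on Day 90 at Day 56, while a Day 70 flare recorded at that same visit would count.

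Take the same five flares and three deaths, with nobody stopping, and let 5 of the 10 flare-free subjects be seen after Day 86. Through Day 55 the incidence is 3/18, with 12/18 of the mass remaining. Censoring those five on Day 56 leaves 7 at risk, so the last two flares carry (12/18)/7 = 0.0952 each. Incidence = 0.1667 + 2 × 0.0952 = 35.7%, against a correct 27.8%. Taking the earlier of Day 86 and the last staging at any visit puts these five back at Day 86 and restores 27.8%.

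**The case against.** The strongest case is that little depends on this rule.

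- **Reporting.** The abbreviated report omits flares and only lists immunosuppression use. This stands, and it is the main limit. What remains is the protocol analysis, if it is run, and the SAP 7.4 interim summary, which covers other efficacy endpoints up to Day 56 and excepts only overall survival and non-relapse mortality.
- **Narrow path.** Subjects are asked to keep attending after stopping treatment, and early termination staging is sought. An unanswered call is not a contact. Protocol 6.5.2 accepts the early termination visit in place of Day 360 data, so such a subject may have no later contact. The affected subject stops staging before Day 86 and is reached afterwards, and an unseen flare is possible. This stands; the group may be small.
- **Size.** At an assumed 5-10% stopping the bias is small beside sampling error. For scale, 5/18 has an exact 95% interval of 9.7% to 53.5%. No hypothesis is tested. This also stands.

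A reader might infer more than the documents support:

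- **That non-relapse mortality is biased too**, because SAP 7.2.2.8 points to flare methods. That endpoint is death, for which contact does establish status, and SAP 5.1.2.9 states its censoring separately. The missing cross-reference is a different defect.
- **That any cohort with more missed visits is more biased.** A subject who misses visits and returns has a later staging date and is not affected.
- **That sicker subjects are the ones who stop attending.** This is plausible, but neither document says so.

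**Conclusion.** The point holds. Protocol 13.7.6 applies a survival censoring rule to an endpoint that contact alone cannot establish, and neither document corrects it. The direction is certain: flare incidence can only be understated.

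The size cannot be derived from the documents. With assumed flare incidence of 20-40% and 20% mortality by Day 86, and with every subject who stops being contacted later, it is about 0.5 to 2 points at 5-10% stopping and up to about 6.5 points at 30%.

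Practical impact is limited. It would be too strong to say that the trial's reported results are biased, because the abbreviated report contains neither a flare estimate nor a summary of immunosuppression discontinuation. The flaw applies wherever the protocol analysis or the SAP 7.4 interim summary is produced.

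**What to change.** - **13.7.6:** censor subjects alive without a flare at the earlier of Day 86 and their last GVHD staging with medication data at any visit. A subject staged flare-free after Day 86 is then censored at Day 86. Telephone-only contacts do not extend flare follow-up. Death remains the competing event.
- **13.7.7:** censor at the earlier of the analysis day and the last visit at which immunosuppressant use was recorded.
- **13.7.5 and 13.7.8:** state that overall survival and non-relapse mortality do not adopt staging-based censoring; otherwise valid vital-status follow-up would be lost.
- **Medication data:** reconcile Protocol 8.2, which ends general medication recording 30 days after the last dose (Day 49 + 30 = 79, or Day 52 + 30 = 82), with 10.2.5, 10.2.6 and Tables 3 and 4, which record it at visits including Day 86. The new rule needs the latter.

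The cost is a few sentences, using dates already scheduled for collection, and slightly wider confidence intervals. Bias is reduced but not removed if sicker subjects stop attending. A small part also remains where a subject dies after staging has stopped, since an unseen flare may have come before the death.
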